## **9.9 MISSING DATE INFORMATION FOR ADVERSE EVENTS**

The following imputation rules apply to cases in which the start date is incomplete (i.e., partial missing) for adverse events.

- a. **If AEs occurred during the Screening or Pretreatment Period (i.e., the Screening or Pretreatment Period is checked on the AE eCRF)**

### **Missing day and month**

- If the year is the same as the year of the date of informed consent, then the day and month of the date of informed consent will be assigned to the missing fields.
- If the year is prior to the year of the date of informed consent, then December 31 will be assigned to the missing fields.
- If the year is after the year of the date of informed consent, then January 1 will be assigned to the missing fields.

### **Missing month only**

- The day will be treated as missing and both month and day will be replaced according to the above procedure.

### **Missing day only**

- If the month and year are the same as the month and year of the date of informed consent, then the date of informed consent will be assigned to the missing day.
- If either the year is before the year of the date of informed consent or if both years are the same but the month is before the month of the date of informed consent, then the last day of the month will be assigned to the missing day.
- If either the year is after the year of the date of informed consent or if both years are the same but the month is after the month of the date of informed consent, then the first day of the month will be assigned to the missing day.

If the stop date is complete and it is before the date of randomization and the imputed start date as above is after the stop date, the start date will be imputed by the stop date. If the stop date is complete and it is on or after the date of randomization and the imputed start date as above is after the stop date, the start date will be imputed by the date immediately before the date of randomization.

If the start date is completely missing, then the date of informed consent will be used to impute the start date.

b. **If AEs occurred during the Treatment Period (i.e., the Treatment Period is checked on the AE eCRF)**

### **Missing day and month**

- If the year is the same as the year of the date of the first dose of double-blind study drug, then the day and month of the date of the first dose of double-blind study drug will be assigned to the missing fields.
- If the year is prior to the year of the date of the first dose of double-blind study drug, then December 31 will be assigned to the missing fields.
- If the year is after the year of the date of the first dose of double-blind study drug, then January 1 will be assigned to the missing fields.

### **Missing month only**

- The day will be treated as missing and both month and day will be replaced according to the above procedure.

### **Missing day only**

- If the month and year are the same as the month and year of the date of the first dose of double-blind study drug, then the date of the first dose of double-blind study drug will be assigned to the missing day.
- If either the year is before the year of the date of the first dose of double-blind study drug or if both years are the same but the month is before the month of the date of the first dose of double-blind study drug, then the last day of the month will be assigned to the missing day.
- If either the year is after the year of the date of the first dose of double-blind study drug or if both years are the same but the month is after the month of the date of the first dose of double-blind study drug, then the first day of the month will be assigned to the missing day.
- If the stop date is complete and the imputed start date as above is after the stop date, the start date will be imputed by the stop date.
- If the start date is completely missing and the stop date is complete, then the following algorithm is used to impute the start date:
- If the stop date is after the date of the first dose of double-blind study drug, the date of the first dose of double-blind study drug will be assigned to the missing start date.
- If the stop date is before the date of the first dose of double-blind study drug, the stop date will be assigned to the missing start date.

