### **7.11.1 Adverse Events**

Adverse events will be coded by system organ class and preferred term using the MedDRA dictionary, version 18.

An AE that occurs during the Treatment Period will be considered a treatment-emergent adverse event (TEAE) if it started after the first dose of double-blind study drug or was present prior to the date of the first dose of double-blind study drug but increased in severity after the first dose of double-blind study drug. If more than 1 AE was reported before the first dose of double-blind study drug and coded to the same preferred term, the AE with the greatest severity will be used as the benchmark for comparison with the AEs occurring during the Treatment Period. An AE that occurs more than one day after the date of the last dose of double-blind study drug will not be considered as a TEAE.

The number and percentage of patients reporting TEAEs in each treatment group will be tabulated by system organ class (SOC) and preferred term and further categorized by severity and relationship to the study drug. If a patient has more than 1 AE coded to the same preferred term, the patient will be counted only once for that preferred term using the highest severity and closest relationship to study drug for the summarization by severity and relationship to study drug, respectively.

The incidence of common ( $\geq 2\%$  of patients in any treatment group) TEAEs will be summarized by preferred term and treatment group for the Treatment Period.

A serious adverse event (SAE) that occurred between the date of the first dose of double-blind study drug and 30 days after the date of the last dose of double-blind study drug, inclusive, will be considered an on-therapy SAE. The number and percentage of patients who have on-therapy SAEs will be summarized by preferred term and treatment group. In addition, the incidence of on-therapy SAEs that led to death will be summarized separately by preferred term for each treatment group.

The number and percentage of patients in the Safety Population who have AEs leading to premature discontinuation of the study drug will be summarized by preferred term and treatment.

For patients experiencing a TEAE coded as diarrhea, the number of days from first dose of study drug for the Treatment Period to the onset date of the first occurrence of treatment-emergent diarrhea during the Treatment Period will be summarized by treatment group using descriptive

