statistics. In addition, the incidence of treatment-emergent diarrhea by time of first onset for the Treatment Period will be calculated for each treatment group.

For the Screened Population, listings will be presented for patients who died, patients with SAEs, and patients with AEs leading to premature discontinuation, if any.

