## 8. CHANGES FROM ANALYSES PLANNED IN THE PROTOCOL

- a. For the key efficacy parameters Weekly Change from Baseline in Abdominal Pain and Weekly Change from Baseline in CSBM Frequency, the protocol states:

*Additional exploratory comparisons between the linaclotide doses (DR1, DR2) and linaclotide IR,* [REDACTED]

[REDACTED] All other comparisons between linaclotide dose (DR1, DR2, and IR) will be performed descriptively.

- b. For 6/12 Week APC+1 Responder rate, the protocol states:

*If the overall CMH statistic reaches statistical significance ( $\alpha = 0.05$ ), the tested formulation will be considered efficacious and the nature of the dose response will be explored among the individual linaclotide DR doses within the formulation.* [REDACTED]

The SAP clarifies statistical inference compares Placebo to each DR1 and DR2 doses only, regardless of the overall trend significance. All other treatment comparisons will be descriptive in nature.

- c. For each 6/12 Week and 9/12 Week responder endpoint defined in the protocol, a corresponding “Sustained Responder” was added. Each new ‘Sustained Responder’ parameter will be presented and analyzed as described in Sections [7.9.1.1](#) and [7.9.1.2](#)

- d. For the analyses of the 12-week Change from baseline, the protocol states:

[REDACTED]  
[REDACTED] All other comparisons between linaclotide dose (DR1, DR2, and IR) will be performed descriptively.

- e. For all responders in the “Other Efficacy Endpoint” section, the protocol states:

*All categorical responder parameters (e.g., Weekly CSBM +1 Responder) will be analyzed utilizing the same methods defined above for the key efficacy measure 6/12 Week APC +1 Responder.*

The SAP clarifies statistical inference compares Placebo to each DR1 and DR2 doses only. All other treatment comparisons will be descriptive in nature.

- f. For patients experiencing a TEAE coded as diarrhea, analyses of the number of days from first dose of study drug for the Treatment Period to the onset date of the first occurrence of treatment-emergent diarrhea during the Treatment Period listed in the SAP were not identified in the protocol.

- g. The endpoints and analyses of 6/12 and 9/12 Week Adequate Relief were not specified in the protocol.

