## **9.8 MISSING RELATIONSHIP TO STUDY DRUG FOR ADVERSE EVENTS**

If the relationship to study drug is missing for an AE started on or after the date of the first dose of double-blind study drug, all efforts should be made to obtain the date from the investigator. If it is still missing after all efforts, a causality of “Related” will be assigned in the corresponding analysis derived data set. The imputed values for the missing relationship to double-blind study drug will be used only for incidence summary, while the actual missing values will be presented in data listings.

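### Imputed start dates for partially dated adverse events are not kept out of the diarrhea onset summaries, where they can only make post-dose onset look earlier

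*SAP*

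**What the plan says.** The scope sentence of SAP 9.9 is general: "The following imputation rules apply to cases in which the start date is incomplete (i.e., partial missing) for adverse events". Part (b) covers events marked on the eCRF as occurring in the Treatment Period:

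- Day missing, month and year of first dose: "then the date of the first dose of double-blind study drug will be assigned to the missing day".
- Day missing, later month: the 1st of that month.
- Day and month missing, year of first dose: the first-dose date. Later year: January 1.
- Month alone missing: the recorded day is set aside and the day-and-month rule applies.
- Start wholly missing, stop date after first dose: the first-dose date.
- Known month or year before first dose: the last day of that month, or December 31.

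SAP 7.11.1 then describes, by treatment group, the number of days from first dose "to the onset date of the first occurrence of treatment-emergent diarrhea". It adds that "the incidence of treatment-emergent diarrhea by time of first onset for the Treatment Period will be calculated". SAP Section 8, item f, records that the onset analyses of "treatment-emergent diarrhea during the Treatment Period listed in the SAP were not identified in the protocol".

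SAP 9.8 confines imputed causality: "The imputed values for the missing relationship to double-blind study drug will be used only for incidence summary". SAP 9.7 likewise directs imputed severity to the incidence summary, though without the word only. SAP 9.9 has no comparable sentence. Neither document flags imputed onset dates, excludes them from the onset summaries or tests their effect.

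**The concern.** An early imputed date is a sensible way to decide whether an event is treatment-emergent, because a doubtful event is then attributed to treatment. Used as a measured onset time, the same date carries an error of known sign.

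The onset summary matters to this trial. Protocol Section 3 reports diarrhea as the most frequent treatment-emergent event with linaclotide IR (19.8%, against 3.0% on placebo), and the delayed release formulations are meant to limit fluid secretion. Early placement would inflate Day 1 and pull the days-to-onset statistics down. Having one rule for all arms does not fully cancel this, because the shift is larger where true onset is later; differences in timing between arms would tend to be compressed.

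Uncertain onset days are plausible. The follow-up call made within 48 hours of first dose may be dropped after the first 40 calls, and later scheduled AE questioning is at Weeks 4, 8 and 12.

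**Working it through.** The plan states no figure on this point, so there is none to reproduce.

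**Direction.** Take an event that truly begins on or after first dose.

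- The first-dose date cannot be later than the true date.
- The 1st of the recorded later month, and January 1 of the recorded later year, cannot be later than a true date in that month or year.
- The rule that resets a start lying after the stop date is not triggered, because the imputed start is at or before the true start.
- The branches that take the latest day apply only to dates before first dose.

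So the error is zero or towards earlier onset.

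**Worked dates** (illustrative first dose 20 November 2015):

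- Day missing, true onset 27 November (Day 8): imputed Day 1.
- Day missing, true onset 18 December (Day 29): imputed 1 December, Day 12.
- Day missing, true onset 1 January (Day 43): stays Day 43.
- Day and month missing, true onset 18 December (Day 29): imputed Day 1.
- Day and month missing, true onset 15 January (Day 57): imputed 1 January, Day 43.

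**Simulation.** The 9.9(b) rules were applied to 100,000 post-dose onsets per scenario. Assumptions: first-dose dates uniform over a year; onset exponential with mean 7, 14 or 28 days, truncated to the first 86 days, or uniform over 86 days. The documents give no onset distribution. No onset moved later in any scenario.

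| | Mean 7 d | Mean 14 d | Mean 28 d | Uniform |
|---|---|---|---|---|
| True onset on Day 1 | 13.2% | 6.9% | 3.7% | 1.2% |
| Day missing: imputed to Day 1 | 79.1% | 61.1% | 42.3% | 18.3% |
| Day missing: date unchanged | 16.0% | 9.9% | 6.8% | 4.4% |
| Day missing: mean shift earlier (days) | 4.9 | 7.8 | 10.3 | 12.9 |
| Day and month missing: imputed to Day 1 | 98.2% | 96.4% | 93.6% | 88.3% |
| Day and month missing: mean shift (days) | 6.4 | 12.8 | 22.0 | 39.1 |

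A wholly missing start with a stop date after first dose always becomes Day 1.

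**Effect on the median onset day**, by assumed share of events lacking only the day:

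| Share | Mean 7 d | Mean 14 d | Mean 28 d | Uniform |
|---|---|---|---|---|
| 0% | 5 | 10 | 19 | 44 |
| 5% | 5 | 10 | 18 | 43 |
| 10% | 5 | 9 | 18 | 42 |
| 20% | 4 | 8 | 16 | 41 |

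The movement is 0 to 3 days.

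**Cases per arm.** With 65 patients, 65 × 0.198 = 12.87 cases at the IR rate and 65 × 0.030 = 1.95 at the placebo rate. At the IR rate, 5% to 20% partial dates is 12.87 × 0.05 = 0.64 to 12.87 × 0.20 = 2.57 events. Excess Day 1 cases = partial events × (share imputed to Day 1 − share truly on Day 1). With only the day missing, this runs from 0.64 × (0.183 − 0.012) = 0.11 to 2.57 × (0.791 − 0.132) = 1.7 cases in an arm of about 13.

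**Status of an event placed on the first-dose date.** SAP 7.11.1 counts an event as treatment-emergent if it started after the first dose. Protocol 5.7.9.1 counts one not present before the first-dose date. An event imputed to that date, with no time, clearly qualifies under the protocol wording but not under the SAP wording. It could count as Day 1 or drop out.

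**The case against.** The case on the other side is that this is a residual rule with little to act on.

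- SAP 7.11.1 does not say that imputed dates enter the onset summaries, and SAP Section 1 places table specifications in a separate document that may deal with them. This stands: entry is inferred from the unrestricted scope of 9.9.
- Partial dates should be few. Protocol 5.6.1 and 5.6.2 provide for queries and completeness checks, Protocol 5.5.3.2.1 requires AEs raised between visits to be documented, and bowel movements go into the eDiary with day and time. This stands as a reason to expect a small effect. It does not change the sign of the error in the dates that remain.
- The size rests on assumptions. The share of partial dates is not given, and Protocol Section 3 says the frequency of gastrointestinal effects with the DR formulations is still to be determined, so 13 cases per DR arm is a borrowed figure. This stands.
- Treating every partial date as unknown would discard a recorded month. This stands, and the fix keeps the month.

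A reader might infer that every imputed diarrhea event moves earlier, usually to Day 1. The rules do not support that. Some events keep their true date (about 4-16% when only the day is missing). The missing-day rule gives Day 1 only within the calendar month of first dose, 18-79% of events under the assumed onset patterns.

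**Conclusion.** The point holds as a gap with a one-directional error. Followed as written, SAP 9.9(b) lets a classification date serve as an onset time, and for post-dose onsets that date is either right or too early. Some events would collect on Day 1.

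The size is probably small and cannot be fixed from the documents. The median shift of 0-3 days rests on three assumptions: 5-20% partial dates, only the day missing, and the onset patterns above. Missing months would shift the affected events further, and no partial dates would mean no effect.

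The output is descriptive. It would be wrong to read this as biasing a treatment test, since none is planned on onset time. Overall diarrhea incidence does not depend on the onset day, apart from the unsettled status of events placed on the first-dose date.

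**What to change.** 1. State in SAP 9.9 that imputed start dates serve to classify events as treatment-emergent. Make clear in 7.11.1 that an event imputed to the first-dose date counts as treatment-emergent.
2. Base the days-to-onset statistics on complete dates, and show the same display with imputed dates included as a check.
3. In the incidence-by-onset table, flag partially dated first events. Put each in its interval where the recorded month determines it, and otherwise in a row for onset day unknown, so that total incidence is unchanged. SAP 7.11.1 does not list the intervals, so they should be named at the same time, together with the choice of first episode when one is fully dated and another is not.

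The cost is a few sentences of SAP text, one table row and one supporting display. The downside is that the main days-to-onset statistics lose the few partially dated events and become a complete-date description; the check in step 2 shows whether that matters.

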## **9.10 MISSING DATE INFORMATION FOR PRIOR OR CONCOMITANT MEDICATIONS**

For prior or concomitant medications, incomplete (i.e., partially missing) start date and/or stop date will be imputed. When the start date and the stop date are both incomplete for a patient, impute the start date first.

### **9.10.1 Incomplete Start Date**

The following rules will be applied to impute the missing numerical fields. If the stop date is complete and the imputed start date is after the stop date, then the start date will be imputed using the stop date.

#### **Missing day and month**

- If the year of the incomplete start date is the same as the year of the date of the first dose of double-blind study drug, then the day and month of the date of the first dose will be assigned to the missing fields.
- If the year of the incomplete start date is prior to the year of the date of the first dose of double-blind study drug, then December 31 will be assigned to the missing fields.

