#### **5.4.7 Concomitant Medicines**

A complete list of drugs that are conditionally allowed and drugs that are not allowed as concomitant medicines for either episodic or chronic use or as Rescue Medicine is provided in [Appendix II](#). During the Pretreatment and Treatment Periods, patients may use dispensed, protocol-permitted laxatives (bisacodyl tablets or suppositories) as Rescue Medicine when at least 72 hours have passed since their previous BM or when their symptoms become intolerable. In order to qualify for randomization into the Treatment Period, patients must not have used Rescue Medicine on the calendar day before the Randomization Visit and on the day of the Randomization Visit up until the time of the clinic visit. Patients must agree to refrain from using Rescue Medicine from the time they arrive at the clinic for the Randomization Visit through the calendar day after randomization.

At the Screening Visit, all ongoing medicines or investigational products taken by the patient, and past use of certain IBS-C or CIC (approved or unapproved) prescription medications

(including tegaserod [Zelnorm®], prucalopride, plecanatide, linaclotide [Linzess®] and lubiprostone [Amitiza®]), even if not ongoing at the time of the Screening Visit, will be recorded. Any over-the-counter or prescription laxatives, suppositories, or enemas used to treat IBS-C may not be used during the Pretreatment and Treatment Periods and may not be used on the calendar day before the Pretreatment Visit. Other prohibited medicines may not be used during the Pretreatment and Treatment Periods and may not be used during the 14 calendar days before the Pretreatment Visit (refer to [Appendix II](#)). Thereafter, any changes in concomitant medicines or new medicines added will be recorded on the eCRF. Concomitant medicines will be recorded at study visits throughout the entire study. Rescue Medicine will be documented by the patient via eDiary.

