### **7.2 PROTOCOL DEVIATIONS**

Protocol deviations and Important Protocol Deviations (IPD) will be identified and documented for all randomized patients prior to unblinding through programmatic checks of the study data

and select individual data reviews. IPDs will be determined based on review of all protocol deviations and protocol deviation categories (i.e., Use of Disallowed Medication) performed by members of the Ironwood Clinical Trials team, including but not limited to the Clinical Medical Researcher and study Biostatistician. Deviations to be reviewed include, but are not limited to:

- those who entered the study even though they did not satisfy the entry criteria;
- those who developed withdrawal criteria during the study but were not withdrawn;
- those who received the wrong treatment or incorrect dose;
- those who received an excluded concomitant treatment.

The number and percentage of subjects with IPDs will be presented by study treatment and IPD category. Protocol deviations and IPDs will be provided by patient in data listings.

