## 7.7 PRIOR AND CONCOMITANT MEDICATION

Prior medication is defined as any medication taken before the date of the first dose of double-blind study drug. Concomitant medication is defined as any medication taken on or after the date of the first dose of double-blind study drug during the Treatment Period. Medications started after the date of the last dose of double-blind study drug will not be considered concomitant medications.

Both prior and concomitant medications will be coded by drug name and therapeutic class using WHO Drug Dictionary version B2 March 2015. The use of prior and concomitant medications will be summarized for the Safety Population by the number and percentage of patients in each treatment group receiving each medication within each therapeutic class. If a patient took a specific medication multiple times or took multiple medications in the same category (based on Anatomical-Therapeutic-Chemical classification), that patient would be counted only once for the coded drug name or therapeutic class. The use of per-protocol rescue medicines is collected separately the eDiary and will be summarized as described in Section 7.9.2.

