### **9.10.2 Incomplete Stop Date**

The following rules will be applied to impute the missing numerical fields. If the date of the last dose of double-blind study drug is missing, replace it with the last diary call date. If the imputed

stop date is before the start date (imputed or non-imputed start date), then the imputed stop date will be equal to the start date.

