### **Missing day and month**

- If the year of the incomplete stop date is prior to the year of the date of the last dose of double-blind study drug, then December 31 will be assigned to the missing fields.

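### Medicine entries with a partial start date in the first-dose year (or month) and no complete earlier stop date are imputed to start on Day 1 and drop out of the prior-medication table

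*SAP*

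**What the plan says.** Protocol 5.4.7 has sites record, at Screening, all ongoing medicines and past use of certain IBS-C or CIC drugs (tegaserod, prucalopride, plecanatide, linaclotide, lubiprostone). For the past drugs it adds "even if not ongoing at the time of the Screening Visit, will be recorded".

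SAP 7.7 then sorts medicines by date: "Prior medication is defined as any medication taken before the date of the first dose of double-blind study drug". A concomitant medicine is one taken on or after that date during the Treatment Period. A medicine can be both.

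SAP 9.10 fills in incomplete dates as follows.

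- Order: "When the start date and the stop date are both incomplete for a patient, impute the start date first".
- Start with only the year known, equal to the first-dose year: "then the day and month of the date of the first dose will be assigned to the missing fields".
- Start with only the year known, and an earlier one: 31 December of that year is used, so the start falls before first dose.
- Start with month and year known, both equal to those of the first dose: the day of first dose is used.
- Cap on the start: if the stop date is complete and the imputed start falls after it, the start takes the stop date. Partial stop dates have no such cap.
- Stop with only the year known: one rule, which opens "If the year of the incomplete stop date is prior to the year of the date of the last dose of double-blind study drug" and assigns 31 December. The month-and-year rule likewise covers only months before the last-dose month. Nothing covers the same year or the same month.
- Stop that would fall before the start: "then the imputed stop date will be equal to the start date".

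**The concern.** The rules anchor every medicine to the first and last dose and make no use of the visit at which it was recorded. An entry made at Screening describes something that had already happened by then. If its start date is partial and falls in the first-dose year, the rules can still place it on Day 1.

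At stake is the accuracy of the by-arm prior and concomitant medication tables. Prior IBS-C treatment would be understated, and a drug that had stopped before Screening would appear as taken during treatment. For a stable background medicine, the table would suggest that it began with study drug. Appendix II allows several classes, such as antidepressants and proton pump inhibitors, only on a dose stable for 30 days before Screening, so a Day 1 start would contradict the eligibility record.

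**Working it through.** The plan gives no figure to reproduce here, so the check is to apply the rules as written.

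**Inputs.** The start, cap and stop rules come from SAP 9.10 to 9.10.2, and the definitions of prior and concomitant from SAP 7.7. Calendar dates are assumed: first dose 15 Jun 2016, last dose 84 days later, 7 Sep 2016.

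**Formulas.** Prior if imputed start < first-dose date. Concomitant if the medicine was taken on or after the first-dose date. A blank stop is read as ongoing, which the SAP does not state.

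| Recorded start | Recorded stop | Imputed start | Imputed stop | Prior | Concomitant |
|---|---|---|---|---|---|
| 2016 | 20 Mar 2016 | 20 Mar 2016 | 20 Mar 2016 | yes | no |
| 2016 | Mar 2016 | 15 Jun 2016 | 31 Mar, moved to 15 Jun 2016 | **no** | **yes** |
| 2016 | 2016 | 15 Jun 2016 | blank, no rule | **no** | **yes**, if blank = ongoing |
| 2016 | none, ongoing at Screening | 15 Jun 2016 | none | **no** | yes |
| 2015 | Mar 2016 | 31 Dec 2015 | 31 Mar 2016 | yes | no |
| 2015 | 2015 | 31 Dec 2015 | 31 Dec 2015 | yes | no |
| 2015 | 2016 | 31 Dec 2015 | blank, no rule | yes | yes, if blank = ongoing |

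In row 2 the site knows that the drug stopped in March, and the rules overwrite this with June. Row 4 is the medicine already in use at Screening. It is properly concomitant but is wrongly lost from prior. The same happens if it later gets a complete stop date after first dose, because the cap acts only when the stop precedes the imputed start. In row 7 prior status is correct, and only the missing stop rule matters.

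**Across a year end.** First dose 16 Nov 2015, last dose 8 Feb 2016, entry 2015 to 2015: the start becomes 16 Nov 2015 and the stop 31 Dec 2015, so not prior and concomitant.

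**Enumeration.** Year-only starts were run for every first-dose date in 2016, with true stops 16 to 719 days before first dose and start years 2014 to 2016.

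- Complete stop date: 0 of 513,918 cases lost from prior (61,425 same-year plus 452,493 earlier-year).
- Earlier-year start: 0 of 452,493 lost, for each type of stop date.
- Same-year start with a month-and-year stop: 61,425 of 61,425 lost. With a year-only stop: 61,425 of 61,425 lost.

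These are enumerated cases, not expected frequencies. They show that the outcome depends wholly on the type of date.

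**Size of the date error for past IBS-C drugs.** Exclusion 20 bars commercial linaclotide in the 30 days before Screening, and Screening is no later than Day -15. An imputed Day 1 start is therefore wrong by about 30 + 15 = 45 days or more. Lubiprostone has a 14-day washout before a Pretreatment Visit no later than Day -14, so the error is about 14 + 14 = 28 days or more.

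**The case against.** The strongest case against the point is that the failing combination is narrow. Old, poorly remembered use usually belongs to an earlier calendar year, which the 31 December rule handles correctly. For recent use, sites have to check the linaclotide exclusion and the washouts, and a bare year would not settle those, so fuller stop dates are likely. The eCRF is not among the documents, and neither the protocol nor the SAP says that past use is entered with start and stop dates in the records that SAP 9.10 imputes. All of this stands. It limits how often the problem arises, not what the rule does when it does.

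It may also be said that counting doubtful medicines as concomitant is a cautious convention. That does not justify removing them from prior, since SAP 7.7 lets a medicine be both. Nor does it justify overriding a status already collected at Screening. SAP 9.9 avoids this for adverse events by imputing according to the period checked on the eCRF, with informed consent as the anchor before treatment.

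A reader might infer more than the documents support:

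- *That every year-only start on a stopped IBS-C drug becomes Day 1.* It does not: earlier-year starts and complete stop dates before first dose are handled correctly.
- *That false important deviations follow.* SAP 7.2 lists "those who received an excluded concomitant treatment" among the deviations to review, but does not say that the checks use imputed dates. It also provides for team review before unblinding.
- *That the results would look confounded by another IBS-C drug.* The dates feed descriptive counts, and the misdated use precedes randomization, so no systematic difference between arms is expected.

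**Conclusion.** The rule is wrong as written, and the consequence is minor. A partial start date in the first-dose year (year only) or first-dose month (month and year) becomes the first-dose date unless a complete earlier stop date prevents it. A medicine stopped before Screening, with an incomplete stop date, is then dropped from the prior table and shown as concomitant; where its stop stays blank, this assumes that a blank is read as ongoing. A medicine already in use at Screening is dropped from the prior table.

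Every entry of that type is affected, but the documents give no basis for estimating how many there are. The conclusion assumes that such entries reach the dataset to which SAP 9.10 applies. Only the descriptive medication summaries change. Spontaneous bowel movement status rests on rescue and laxative use reported in the eDiary, and no efficacy analysis is tied to these imputed dates.

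**What to change.** Amend SAP 9.10 as follows.

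(a) Extend the cap to partial stop dates: the imputed start may not exceed the latest date compatible with the partial stop, and a stop is not moved past that date. In row 2 of the table, both dates become 31 Mar 2016 and the entry is prior only.

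(b) For any medicine recorded at a visit before first dose (Screening, Pretreatment or Randomization), cap the imputed start at that visit's date. If it was recorded as already stopped, cap the imputed stop there too. This is needed for year-only stops, where (a) gives 31 Dec 2016 and does not bind. With Screening on Day -15 (31 May 2016), the row 3 entry becomes 31 May 2016 for both dates, and the row 4 entry starts on 31 May 2016. Because the Randomization Visit is itself Day 1, entries recorded there as already in use or stopped need the cap set at the day before first dose, or they would still fail the definition of prior.

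(c) Add a rule for a stop date in the same year or month as the last dose, for example the last-dose date, subject to (a) and (b).

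(d) Keep the present first-dose and last-dose rules for medicines first recorded after first dose.

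The cost is a few lines of SAP text and programming before unblinding, with no new data collection. The drawback is that the recording visit or the ongoing flag must be carried into the analysis dataset.
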